2.7. Total cardiovascular risk estimation (Catapano et al., 2016)

Very high risk	Subjects with any of the following: 
• Documented cardiovascular disease (CVD), clinical or unequivocal on imaging. Documented CVD includes previous myocardial infarction (MI), acute coronary syndrome (ACS), coronary revascularization (percutaneous coronary intervention (PCI), coronary artery bypass graft surgery (CABG)) and other arterial revascularization procedures, stroke and transient ischaemic attack (TIA), and peripheral arterial disease (PAD). Unequivocally documented CVD on imaging is what has been shown to be strongly predisposed to clinical events, such as significant plaque on coronary angiography or carotid ultrasound.• DM with target organ damage such as proteinuria or with a major risk factor such as smoking, hypertension or dyslipidemia.• Severe CKD (GFR <30 mL/min/1.73 m²).• A calculated SCORE $\geq 10\%$ for 10-year risk of fatal CVD.
High risk	Subjects with: 
• Markedly elevated single risk factors, in particular cholesterol >8 mmol/L (>310 mg/dL) (e.g. in familial hypercholesterolaemia) or BP $\geq 180/110$ mmHg.• Most other people with DM (some young people with type 1 diabetes may be at low or moderate risk).• Moderate CKD (GFR 30–59 mL/min/1.73 m²).• A calculated SCORE $\geq 5\%$ and <10% for 10-year risk of fatal CVD.
Moderate risk	Subjects are considered to be at moderate risk when their SCORE is $\geq 1\%$ and <5% at 10 years.
Low risk	The low-risk category applies to individuals with SCORE <1% for 10-year risk of fatal CVD.

2.8. Recommendations for lipid management in patients with moderate to severe chronic kidney disease (Catapano et al., 2016). 2016 ESC/EAS Guidelines for the Management of Dyslipidaemias

Recommendations	Class	Level
Patients with stage 3–5 CKD have to be considered at high or very high CV risk.	I	A
The use of statins or statin/ ezetimibe combination is indicated in patients with non-dialysis dependent CKD.	I	A
In patients with dialysis-dependent CKD and free of atherosclerotic CVD, statins should not be initiated.	III	A
In patients already on statins, ezetimibe or a statin/ezetimibe combination at the time of dialysis initiation, these drugs should be continued, particularly in patients with CVD.	IIb	C
In adult kidney transplant recipients treated with statins may be considered.	IIb	C

2.9. Recommendations for treatment goals for low-density lipoprotein-cholesterol (Catapano et al., 2016)

Recommendation	Class of recommendation	Level of evidence
In patients at VERY HIGH CV risk, an LDL-C goal of <1.8 mmol/L (70 mg/dL) or a reduction of at least 50% if the baseline LDL-C is between 1.8 and 3.5 mmol/L (70 and 135 mg/dL) is recommended.	I	B
In patients at HIGH CV risk, an LDL-C goal of <2.6 mmol/L (100 mg/dL), or a reduction of at least 50% if the baseline LDL-C is between 2.6 and 5.2 mmol/L (100 and 200 mg/dL) is recommended.	I	B
In subjects at LOW or MODERATE risk, an LDL-C goal of <3.0 mmol/L (<115 mg/dL) should be considered	IIa	C

2.10. Lipid Measurement in Adults with CKD. (Sarnak et al., 2015). 2013 KDIGO Clinical Practice Guidline for Lipid management in CKD

1.1. In adults with newly identified CKD (including those treated with chronic dialysis or kidney transplantation), we recommend an evaluation with a lipid profile (total cholesterol, LDL cholesterol, HDL cholesterol, triglycerides). (1C)

1.2. In adults with CKD (including those treated with chronic dialysis or kidney transplantation), follow-up measurement of lipid levels is not required for the majority of patients. (Not Graded)

2.1.1. In adults aged \geq 50 years with eGFR $<$ 60 ml/min/1.73 m² but not treated with chronic dialysis or kidney transplantation (GFR categories G3a-G5), we recommend treatment with a statin or statin/ezetimibe combination. (1A)

2.1.2: In adults aged \geq 50 years with CKD and eGFR \geq 60 ml/min/1.73 m² (GFR categories G1-G2), we recommend treatment with a statin. (1B)

2.2: In adults aged 18-49 years with CKD but not treated with chronic dialysis or kidney transplantation, we suggest statin treatment in people with one or more of the following (2A):

- known coronary disease (myocardial infarction or coronary revascularization)
- diabetes mellitus
- prior ischemic stroke
- estimated 10-year incidence of coronary death or non-fatal myocardial infarction > 10%

2.3.1: In adults with dialysis-dependent CKD, we suggest that statins or statin/ezetimibe combination not be initiated. (2A)

2.3.2: In patients already receiving statins or statin/ezetimibe combination at the time of dialysis initiation, we suggest that these agents be continued. (2C)

2.4: In adult kidney transplant recipients, we suggest treatment with a statin. (2B)

2.11. Recommended doses of statins in adults

Recommended doses of statins in adults			
	ACC/AHA Recommendations for eGFR > 60 mL/min/1.73 m ²		KDIGO Recommendations for e-GFR < 60 mL/min/1.73 m ²
	High-Intensity Statin	Moderate-Intensity Statin	
Atorvastatin	40-80 mg	10-20 mg	20 mg
Fluvastatin	—	80 mg	80 mg
Lovastatin	—	40 mg	Not studied
Pravastatin	—	40-80 mg	40 mg
Rosuvastatin	20-40 mg	5-10 mg	10 mg
Simvastatin	— ^a	20-40 mg	40 mg
Simvastatin/ezetimibe	—	Not mentioned in ACC/AHA guidelines	20 mg/10 mg

2.12. Simvastatin

- Treat with statins for 1-2 weeks, up to 4-6 weeks, and maintain during long-term treatment.
- Simvastatin largely excreted in the feces. Approximately 10-15% of the drug excreted by the kidney
- Dosage is 5-80 mg/day, in the evening.
- No dosage adjustment is needed in the elderly
- **Contraindications of Simvastatin:**
 - + Active liver disease or unexplained persistent elevations of serum transaminases

- + Pregnancy and lactation
- + Concomitant administration of potent CYP3A4 inhibitors (e.g. itraconazole, ketoconazole, posaconazole, HIV protease inhibitors (e.g. nelfinavir), erythromycin, clarithromycin, telithromycin, and nefazodone)
- + Concomitant administration of gemfibrozil, ciclosporin, or danazol.
- **Unexpected effects of Simvastatin and how to manage unexpected effects**
 - + **Myopathy:** The risk of myopathy is related to dose. In a clinical trial of 41,413 patients treated with simvastatin, 24,747 patients (about 60%) with an average follow-up of at least 4 years, the incidence of myopathy was approximately 0.03%, 0.08% and 0, 61% at doses of 20, 40 and 80 mg/day, respectively.
 - If the patients have muscle aches, weakness or cramps, do CK test. If CK increases (> 5 times) discontinue treatment, re-assess levels within 5 to 7 days.
 - If the muscular symptoms are severe and cause daily discomfort, even if the CK levels are < 5 times normal, consider stopping treatment.
 - + **Elevated liver enzymes:** Continuous elevations (up to > 3 times) liver enzymes have occurred in some patients receiving simvastatin.
 - When simvastatin is discontinued, the level of transaminase usually decreases gradually down to the pre-treatment level.

+ **Diabetes Mellitus**

Some evidence suggests that statins as a class raise blood glucose and in some patients, at high risk of future diabetes, may produce a level of hyperglycemia where formal diabetes care is appropriate. This risk, however, is outweighed by the reduction in vascular risk with statins and therefore should not be a reason for stopping statin treatment.

+ Other side effects: Dizziness, fainting, fast or irregular heartbeat,...

2.13. Ezetimibe

- Ezetimibe inhibits the intestinal absorption of cholesterol, which reduces cholesterol from the small intestine into the liver.
- Dose may be 10-40mg / day
- Ezetimibe is metabolized mainly in the small intestine and liver, excreted in the bile.
- No dosage adjustment in elderly patients, patients with CKD
- Hepatic impairment: EZE is not known in patients with moderate or severe liver failure, should not be used.
- Patients with chronic kidney disease / renal disease
 - + Monotherapy: No need to adjust the dose of Ezetimibe.
 - + Combination with Simvastatin:
 - No dose adjustment of Ezetimibe or simvastatin in patients with GFR ≥ 60 mL/min / 1.73m².
 - In patients with GFR < 60 mL / min / 1.73m²), the dose of Ezetimibe is 10 mg and simvastatin is 20 mg once daily, taken in the evening. Patients should be monitored if higher doses of simvastatin are used.

2.14. New York Heart Association class III (McMurray et al., 2012)

Classification of heart failure symptoms

Class I	People whose physical activity is not limited. Ordinary physical activity does not cause undue fatigue, heart palpitations, trouble breathing, or chest pain.
Class II	People who have some limitation on physical activity. They are comfortable at rest, but ordinary physical activity causes fatigue, heart palpitations, trouble breathing, or chest pain.
Class III	People who have a marked limitation on physical activity. They are comfortable at rest, but less-than-ordinary physical activity causes fatigue, heart palpitations, trouble breathing, or chest pain.
Class IV	People who are unable to carry on any physical activity without discomfort. Symptoms may be present even at rest. If any physical activity is done, discomfort increases.

2.15. 2017 Taiwan lipid guidelines for high-risk patients

LDL-C increased CV risk in patients with CKD. In adults with glomerular filtration rate (GFR) < 60 mL/min/1.73m² without chronic dialysis (CKD stage 3-5), statin therapy should be initiated if LDL-C ≥ 100 mg/dL. Ezetimibe can be added to a statin to consolidate the CV protection in CKD patients (Li et al., 2017)

3. Objective of the research

The target of this study is to focus on mechanisms underlying dyslipidemia in CKD and clinical trial evidence for lipid lowering therapy in patients with CKD via parameters of lipid, oxidative stress, tryptophan degradation as well as renal function, in comparison to statin/ezetimibe therapies in CKD patients with dyslipidemia.

- 1) To verify the effect of lipid lowering therapies on lipid profile and inflammatory status in Vietnamese CKD population. [Time Frame: at the baseline and at 4th month, and one-year following].
- 2) To compare the effect of lipid-lowering regimes (simvastatin mono-therapy and EZE/simvastatin 10/20, EZE /simvastatin 10/40 combination therapy) on lipid profile, oxidative stress indices, Tryptophan degradation, renal parameter, and side effect in Vietnamese CKD patient. [Time Frame: after the 4th month, 8th month and one-year following].

We hope with scientific evidence, doctors will well understand the mechanism, effect, and safety of potential and existing therapies. Therefore, the prescription rate of lipid-lowering drugs and control rate of hyperlipidemia could be increased in CKD

patients. The major purpose is to improve clinical outcomes of CKD patients through the control of hyperlipidemia.

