(1) Do different lipid-lowering drugs (simvastatin monotherapy and ezetimibe/simvastatin combination therapy) have a different impact on the lipid profile, oxidative stress indices, Tryptophan degradation?

(2) Does statin monotherapy or co-administration of ezetimibe ameliorate the renal dysfunction in CKD patients?

(3) How do lipid-lowering therapy effect on lipidemia disorders in patients with CKD by mechanism involved in oxidative stress and tryptophan?

(4) Are the unexpected effects on muscle problem and hepatic enzyme profile of long-term statin monotherapy and statin/ezetimibe combination therapy a big concern?

II. REVIEW OF RESEARCH LITERATURE

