4. METHODOLOGY

4.1. Study design: A prospectively study with clinical trials, 12 months follow up.

4.2. Subject: 30 patients with hypercholesterolemia (LDL-C), stage 3-4 Chronic Kidney Disease, not receiving dialysis and 30 control participants (sex, age-matched)

4.2.1. Inclusion Criteria:

30 patients with following criteria

- CKD in the 3,4 stage (e-GFR: 15-60 ml/min/1.73 m²)
- Presence of proteinuric CKD defined as creatinine clearance >20 ml/min/1.73 m² combined with urinary protein excretion rate >0.3 g/24 h
- LDL cholesterol concentration > 100 mg/dl (2,59 mmol/l)
- Age:
 - + ≥ 50 years old but not treated with chronic dialysis or kidney transplantation
 - + In adults aged 18-49 years with CKD but not treated with chronic dialysis or kidney transplantation, we suggest statin treatment in people with one or more of the following:
 - known coronary disease (myocardial infarction or coronary revascularization)
 - diabetes mellitus
 - prior ischemic stroke
 - estimated 10-year incidence of coronary death or non-fatal myocardial infarction > 10%

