4.4. Time: 3 years (From November 2017 to November 2020)

4.5. Medication:

- Group1: simvastatin 40mg/day 12 months
- Group2: EZE/simvastatin (10/20) mg/day 12 months
- Group3: EZE/simvastatin (10/40) mg/day 12 months

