4.6. Procedure

- Potentially eligible patients attended a screening visit in an internal examination room or internal department of Hue University Hospital for medical history and other eligibility criteria checked.

- Fasting blood samples will be taken for local laboratory assays lipid profile, proteinuria, urea and creatinine, creatine kinase, SGOT, SGPT, total blood count, total haemostasis test

- If the patient satisfies the including criteria, written informed consent obtained 30 enrolled patients will be randomized into 3 groups and will receive one of 3 lipid-lowering therapies at the baseline and continue for 12 months

Group 1: (10 participants) receive 40 mg/day simvastatin (patient No 1, 4, 7...)

Group 2: (10 participants) receive ezetimibe/simvastatin 10/20 mg/day: (patient No 2, 5, 8...)

Group 3: (10 participants) receive ezetimibe/simvastatin 10/40 mg/day: 10/40: (patient No 3, 6, 9...)

- Patients will follow the treatment for 12 months and will be seen in the study clinics for routine follow-up checks and blood test at 4, 8, and 12 months.

- At each follow-up time, study treatment will be continued, unexplained muscle pain and non-study treatment recorded.

Patients are asked for an unscheduled visit if they want to have any additional review.

- If patients are unable or unwilling to attend the follow-up checks, ask them if they have any serious adverse events.

- The blood samples will be sent to Biochemical Department of Sassari University for oxidative stress indices and Tryptophan degradation indices every 4 months.

5. Biochemical analysis

- Serum Creatinine, GFR, urine protein, lipid profile, SGOT, SGPT, CK (Total Cholesterol, LDL-C, HDL-C, TG): Will be done in Hue University hospital/Hue Central Hospital.

+ Total Cholesterol, LDL-C, HDL-C, and TG were measured by enzymatic methods using commercial kits (Boehringer-Mannheim, Mannheim, Germany): Patients must fast for at least 12 hours before the test

+ Serum CK levels were measured by using a fully automated biochemical analyzer (Abbot).

+ Proteinuria

+ Serum urea, creatinine

+ Total cells blood count

+ Total hemostasis test

[Time Frame: at baseline and 4, 8, 12 months of treatment]

- Serum concentrations of Oxidative stress indices (MDA, All/UA, Taurine), Trp degradation indices (Kyn, Trp, Kyn/Trp ratio): Will be done in Sassari University hospital.

MDA, All/UA ratio, taurine, Kyn, Trp were determined by capillary electrophoresis UV detection.

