STATISTICAL ANALYSIS PLAN

LIPID-LOWERING REGIMES IMPROVE OXIDATIVE STRESS, TRYPTOPHAN DEGRADATION IN HYPERCHOLESTEROLEMIA CKD PATIENTS

Date of review: 05th May, 2018

All results will be expressed as mean values (mean SD) or median values (median and range).

The statistical differences between the mean laboratory test results patients and control group will be analyzed by ANOVA one-way statistical analysis or by Student's t-test (with Kolmogorov-Smirnov for normality).

The statistical differences in the effect of each therapy on laboratory mean values will be evaluated by one way repeated measure ANOVA with Bonferroni correction or Dunnet T3 correction, if appropriate.

To compare the differences in the median values of laboratory tests between 3 groups, ANOVA one-way will be applied. If there are statistical differences between 3 groups, we will use deeply ANOVA one-way test to analyze which group is different from another group (with Bonferroni if Levene test ≥ 0.05 or Dunnet T3 if Levene test < 0.05).

Correlation analysis between variables will be performed by Pearson's correlation or Spearman's correlation as appropriate.

Statistical analysis will be performed by using SPSS for Windows, version 20.0 (IBM Corporation; Armonk, NY, USA).

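### Change over visits within an arm is treated as a treatment effect, but every CKD patient is on active drug, so it cannot be separated from regression to the mean, time trend or CKD progression

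*Protocol*

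**What the plan says.** Protocol section 3 sets two objectives. Objective 1 is "To verify the effect of lipid lowering therapies on lipid profile and inflammatory status in Vietnamese CKD population", with a time frame of baseline, month 4 and one year. Objective 2 separately compares the three regimens on lipids, oxidative stress, tryptophan degradation, renal function and side effects. Research question 2, in section I, asks: "Does statin monotherapy or co-administration of ezetimibe ameliorate the renal dysfunction in CKD patients".

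Section 4.5 lists three arms, all active: "Group1: simvastatin 40mg/day 12 months", "Group2: EZE/simvastatin (10/20) mg/day 12 months" and "Group3: EZE/simvastatin (10/40) mg/day 12 months". Section 4.6 confirms that "30 enrolled patients will be randomized into 3 groups and will receive one of 3 lipid-lowering therapies at the baseline". No placebo, untreated, delayed-start or run-in CKD group is described. The 30 controls in section 4.2.3 are matched on age and sex and must have no history of renal failure. No follow-up visits are described for them.

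Entry is restricted by LDL-C ("LDL cholesterol concentration > 100 mg/dl (2,59 mmol/l") and by urinary protein above 0.3 g/24 h (section 4.2.1). Both are measured at the screening visit (section 4.6).

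The SAP states: "The statistical differences in the effect of each therapy on laboratory mean values will be evaluated by one way repeated measure ANOVA". It also compares patients with controls, and compares the three groups by one-way ANOVA with Bonferroni or Dunnett T3 follow-up tests. Neither document mentions a limit on what the within-arm test can show.

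**The concern.** A one-way repeated-measures ANOVA has a single factor, visit. It asks whether the mean changes over time, not why. To read a change as the effect of a drug, one must know how the same kind of patient would have changed without it, and this design never observes that.

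Three other causes of change are present. Patients are selected on high LDL-C and on proteinuria, so both can fall on re-measurement without any drug. Laboratory values can drift over a year. Stage 3-4 CKD can also progress. These act in different directions: regression to the mean in LDL-C or proteinuria looks like benefit, while falling eGFR looks like harm or hides a benefit. At stake is whether Objective 1, and the part of research question 2 about statin alone, can be answered as worded.

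**Working it through.** The documents give no SD, effect size, power or overall significance level, so there is no planned figure to reproduce apart from 30/3 = 10 patients per arm, which agrees with section 4.6. The inputs below are assumptions unless a source is named.

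**1. Which comparisons have an untreated CKD reference?**
- Within arm, over visits: none, because all three arms are active.
- Patients versus controls: none, because controls have no renal failure and no described follow-up.
- Arm versus arm: none is needed. Regression to the mean, time trend and progression are the same in all arms in expectation, so they cancel in the difference.

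**2. Regression to the mean in LDL-C.** Take the cut-off of 100 mg/dl (section 4.2.1), assume a population mean of 110 to 130 mg/dl, SD 30 to 35 and repeat correlation ρ of 0.7 to 0.9, and let the screening value serve as baseline. With z = (100 − mean)/SD,

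expected fall = (1 − ρ) × SD × φ(z)/(1 − Φ(z)).

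- Mean 130, SD 30, ρ 0.9: z = −1.00, ratio 0.2420/0.8413 = 0.288. The fall is 0.1 × 30 × 0.288 = 0.9 mg/dl.
- Mean 120, SD 35, ρ 0.8: z = −0.571, ratio 0.3388/0.7161 = 0.473. The fall is 0.2 × 35 × 0.473 = 3.3 mg/dl.
- Mean 110, SD 35, ρ 0.7: z = −0.286, ratio 0.383/0.612 = 0.625. The fall is 0.3 × 35 × 0.625 = 6.6 mg/dl.

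The mean among selected patients is mean + SD × ratio: about 138.6 mg/dl in the first case and 131.9 in the third. The fall is then 0.9/138.6 = 0.6% to 6.6/131.9 = 5.0%.

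**3. How often the within-arm test is significant with zero drug effect.** Simulation of 10 patients and 4 visits, at an assumed two-sided 5% level, with 20,000 trials per setting:
- No selection and no trend (check): 4.9%.
- LDL-C, wider inputs (mean 100 to 130, SD 35, correlation 0.6 to 0.9): fall of 1.2 to 11.2 mg/dl (0.8% to 8.7%), significant in 5.4% to 17.0%.
- Proteinuria selected above 0.3 g/24 h (log-SD 1, median 0.3 to 1.0 g/24 h, correlation 0.6 to 0.8): apparent fall of 4% to 27%, significant in 5.4% to 17.0%.
- eGFR with no selection, linear decline of 2 to 5 ml/min/1.73 m² a year and within-patient SD 3 to 4: significant in 13% to 88%, from progression alone.

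The LDL-C and proteinuria rows again use the screening value as baseline.

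**4. Research question 2, part by part.** Groups 1 and 3 share simvastatin 40 mg and differ by ezetimibe, so group 3 versus group 1 addresses the ezetimibe part. No group lacks simvastatin, so the statin-monotherapy part has no comparator.

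**5. What the between-arm contrasts can detect.** With 10 per arm, an unadjusted two-sample t-test has 80% power at a standardised difference of about 1.32 (two-sided 5%), or about 1.57 at 0.05/3 for three pairs.

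**The case against.** The plan already contains a valid comparison: Objective 2 and the SAP's test across the three groups. On this view, speaking of each therapy's effect is loose wording that the discussion section of a report could repair. For LDL-C the bias is modest, so an observed fall far beyond these figures could not be put down to regression to the mean. That source also depends on an unstated detail. Section 4.6 describes a screening sample, section 5 lists assays at baseline, and neither says whether these are one draw. With a separate baseline draw the bias would be smaller, and under the equal visit-to-visit correlation assumed above it would vanish in expectation. Finally, sections 2.8 and 2.10 cite guidelines that support statin or statin/ezetimibe in non-dialysis CKD, so an untreated arm may not be available.

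All of this is fair, and it limits the point without removing it. A second baseline draw does nothing about time trend or progression. A valid test elsewhere in the SAP does not make the within-arm test valid for Objective 1.

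A reader might infer more than the documents support:
- That research question 2 claims to verify an effect, or is wholly unanswerable. It is worded as a question, and its ezetimibe part has a randomised contrast.
- That Objective 1 covers renal function and oxidative stress. It names lipid profile and inflammatory status only. The other outcomes are reached through research question 2 and the SAP's general sentence on laboratory values.
- That Objective 2 is undermined. It is not affected by this flaw.
- That any LDL-C fall will be spurious, or that the sponsor will report within-arm change as proof. The documents establish neither.

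**Conclusion.** The point holds for Objective 1, for the SAP sentence on each therapy's effect, and for the statin-monotherapy part of research question 2. That the within-arm test cannot isolate a drug effect follows from the design and needs no assumption. Its size does. Regression to the mean in LDL-C is about 0.9 to 6.6 mg/dl (0.6% to 5.0%) if the screening value is the baseline and the assumed means, SDs and correlations apply. It may be proportionally larger for proteinuria. For eGFR the bias is the whole untreated trend, which the documents do not give; the 13% to 88% range rests on the assumed decline and within-patient SD. No untreated course is given for the oxidative-stress and tryptophan indices either, so the bias there cannot be sized. The trial can proceed as designed, but Objective 1 should not stand as worded.

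**What to change.** - **Protocol:** reword Objective 1, and the statin-monotherapy part of research question 2, to describe change during treatment. Keep the ezetimibe part and tie it to group 3 versus group 1. State whether the baseline sample is the screening sample.
- **SAP, within-arm analysis:** report change from baseline in each arm with a 95% CI, and state that it is not an estimate of treatment effect.
- **SAP, claims of effect:** replace the unadjusted one-way ANOVA with baseline-adjusted contrasts (ANCOVA or a mixed model) among all three randomised arms at months 4, 8 and 12. Group 3 versus 1 gives ezetimibe added at the same simvastatin dose, 3 versus 2 gives simvastatin dose, and 1 versus 2 is a regimen comparison. Retain the planned multiplicity correction for the three pairs.

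The cost is the wording of one objective, one research question and one SAP sentence, plus a modest change to the between-arm analysis. No new arm is needed. The headline claims become weaker, because 10 per arm detects only large differences. Baseline adjustment should help where baseline predicts outcome, but will not change that conclusion. Allocation by patient number (1, 4, 7 and so on, section 4.6) is predictable. That is a separate matter, but these contrasts rely on sound randomisation, so it deserves attention too.

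### The SAP's between-arm test takes one value per patient without naming the visit, and no between-arm analysis combines months 4, 8 and 12; doing so, with baseline adjustment, would be a nearly free gain in precision.

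*Protocol*

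**What the plan says.** Protocol section 4.6 allocates 10 patients to each regimen ("30 enrolled patients will be randomized into 3 groups"). Patients stay on that regimen for 12 months and "will be seen in the study clinics for routine follow-up checks and blood test at 4, 8, and 12 months". Section 5 lists the laboratory markers at baseline and at those three visits, so each patient who completes follow-up supplies three on-treatment values of every marker.

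Section 3, objective 2 is the comparison of regimens. Its timing is "Time Frame: after the 4th month, 8th month and one-year following"; no visit is named as the main one and no average is mentioned.

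The SAP's between-arm statement is: "To compare the differences in the median values of laboratory tests between 3 groups, ANOVA one-way will be applied". Bonferroni or Dunnett T3 post-hoc comparisons follow. The SAP does not say which visit enters, or whether the outcome is a visit value, a change or a mean.

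The only method that uses repeated visits is this one: "The statistical differences in the effect of each therapy on laboratory mean values will be evaluated by one way repeated measure ANOVA". A one-way repeated-measures model has visit as its single factor and no arm term, so on its wording it works within each therapy.

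**The concern.** A one-way ANOVA uses one number per patient. If that number is a single visit's value, the other two on-treatment values play no part in that test of the regimens. If the test is repeated at each visit, every marker gets three answers with no rule for reading them together. With 10 patients per arm and no power calculation in either document, precision is scarce, and the values needed to improve it are already planned. What is at stake is the standard error of the main comparison and the number of tests per marker. The validity of the data collection is not in question.

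**Working it through.** **Plan's own figure.** There is none. The documents give no SD, effect size, power, significance level for treatment tests or between-visit correlation.

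**Inputs.** From protocol section 4.6: 10 per arm, three arms, three on-treatment visits. Assumed: equal SD at every visit, a common correlation r between visits, complete data, and (steps 1 to 4) an arm difference that is the same at all three visits.

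**Step 1: variance of the three-visit mean, no baseline term.** Var(mean)/Var(single visit) = (1+2r)/3, so the equivalent number per arm is 10 × 3/(1+2r).

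| r | variance ratio | equivalent n per arm | gain |
|---|---|---|---|
| 0.30 | 0.533 | 18.75 | +8.8 |
| 0.50 | 0.667 | 15.0 | +5.0 |
| 0.60 | 0.733 | 13.6 | +3.6 |
| 0.75 | 0.833 | 12.0 | +2.0 |
| 0.80 | 0.867 | 11.5 | +1.5 |
| 0.90 | 0.933 | 10.7 | +0.7 |

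If correlation instead decays with time (first-order autoregressive, adjacent r of 0.50 to 0.75), the gain is +6.4 to +2.6.

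**Step 2: baseline as covariate in both analyses.** With the same r between baseline and follow-up, the residual variance is 1−r² for one visit and (1+2r)/3−r² for the mean.
- r = 0.50: 0.750/0.417 = 1.80, equivalent to 18.0 per arm (+8.0).
- r = 0.75: 0.4375/0.2708 = 1.615, equivalent to 16.2 per arm (+6.2).
- r = 0.90: 0.190/0.123 = 1.54, equivalent to 15.4 per arm (+5.4).

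High correlation therefore does not remove the gain once baseline is in the model.

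**Step 3: power for one pair of arms.** Assume a true difference of 1.0 SD and a two-sided t-test on 27 df (26 with baseline). The noncentrality is 1/√(0.2 × variance ratio).
- Single visit: 1/√0.2 = 2.24. Power is 57.8% at the 5% level and 39% at 5%/3, the Bonferroni level for three pairs.
- Three-visit mean at 5%: 75.2% (r = 0.5), 71.1% (0.6), 63.9% (0.8). At 5%/3: 58%, 53%, 45%.
- With baseline, r = 0.6, at 5%: 76.7% for one visit and 94.1% for the mean.

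**Step 4: number of tests.** If the three-arm F test is run at each visit with no true difference, simulation gives a 10% to 13% chance of at least one p < 0.05 per marker (r = 0.8 to 0.5). A single averaged outcome gives 5%.

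**Step 5: when the effect builds.** Suppose the difference is 1/3, 2/3 and 1 SD at months 4, 8 and 12. The average difference is then 2/3 SD. At r = 0.6 without baseline, the noncentrality is 0.667/√(0.2 × 0.733) = 1.74. Power is 39%, against 58% for month 12 alone. With baseline it is 0.667/√(0.2 × 0.373) = 2.44, power 65%, against 77% for month 12 alone. In this case averaging loses power.

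**The case against.** **The plan does not say that visits are tested separately.** A reader might infer that it does. Objective 2 only lists times, and a one-way ANOVA could be run on a patient mean or a change score. This stands: separate tests are the natural reading but an inference, and what is certain is that the outcome is unnamed.

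**Repeated measures are used.** They are, within therapies. The SAP's mention of differences in each therapy's effect, together with Dunnett T3 (a between-group procedure), leaves some doubt whether a mixed design was meant. The one-way label argues against that, and the group main effect of such a design would mix baseline into the treatment comparison.

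**A steady effect is not established.** A reader might take section 2.12 ("Treat with statins for 1-2 weeks, up to 4-6 weeks, and maintain during long-term treatment") as showing a plateau before month 4. The line is about statin treatment and does not say that the effect levels off. It does not mention ezetimibe, oxidative-stress markers or tryptophan markers. Averaging as the sole outcome for those markers is therefore unsupported, and step 5 shows the possible loss.

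**The power gain is partly one of presentation.** If a significant result at any of three visits counts as success, the snapshot approach has about 80% power in the r = 0.6 example, with about 12% false positives. That is correct. Against that practice the benefit is one controlled answer; against a single-visit test it is precision.

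**A gain of 2 to 5 patients depends on r.** It does. It is not a property of this trial that the documents establish, and it would differ by marker.

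**Conclusion.** The point holds as a cheap improvement. The between-arm outcome is not named, and no specified between-arm analysis combines the three on-treatment visits. If the arm difference is stable from month 4 and visits correlate 0.50 to 0.75, the three-visit mean is worth about 5 to 2 extra patients per arm before baseline adjustment. Over r = 0.3 to 0.9 the range is about 9 to 0.7. With baseline as covariate and the same 0.50 to 0.75, it is about 8 to 6. All of this rests on assumed correlations, equal variances and complete visits.

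The documents do not support three stronger readings: that the plan expressly tests each visit separately, that the gain is a fixed 2 to 5 patients, or that every marker has reached a steady effect by month 4.

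**What to change.** Add one paragraph to the SAP, along these lines:

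- *Lipids.* Arms are compared on each patient's mean of the month 4, 8 and 12 values, adjusted for the baseline value. Equivalently when visits are complete, use the visit-averaged arm effect from a mixed model with arm, visit, arm-by-visit and baseline. The mixed model is preferable because it also handles missed visits, which section 4.6 foresees. A simple mean of whatever values are available would weight patients with one, two or three visits alike.
- *Oxidative-stress, tryptophan and renal markers.* The same model is used, and the month-12 contrast is reported alongside the visit average, because no passage supports a plateau by month 4.
- *All markers.* Visit-specific arm estimates with confidence intervals are reported.

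This needs no extra patients, visits or assays and does not touch treatment. The downside is that an effect that builds during the year is diluted in the average and can lose power relative to month 12 (39% against 58% without baseline in the example above). The visit-specific estimates must therefore be kept. Objective 2 should also say how the average and the three listed times relate, since an average answers a somewhat different question from the value at one year.
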